9.5 FINANCIAL DISCLOSURE

All clinical investigators shall disclose to the sponsor sufficient and accurate financial information enabling Spineology to submit complete and accurate certification or disclosure statements as appropriate. The investigator shall promptly update this information should any relevant changes occur during the course of the investigation and for one (1) year following completion of this investigation.

9.6 RADIOGRAPHIC CORE LAB

An independent core lab will be established to perform the required qualitative and quantitative x-ray measurements/assessments. In addition, two (2) core lab radiologists will perform fusion assessments at the 12-month and 24-month time points. A third core lab radiologist will function in the role of adjudicator in the event of discrepant readings between Reviewer 1 and Reviewer 2. For greater detail on core lab responsibilities and assessment, refer to the Radiographic and Core Lab Assessment Protocol provided as **Appendix IV**.

9.7 INVESTIGATIONAL DEVICE USE AND DISPOSITION

As previously stated within this investigation protocol, only sites approved by Spineology Clinical Affairs shall receive investigational product.

For this investigation, SIFS product shall be provided to sites on a ship-in/ship-out basis in support of study cases. Accordingly investigational product shall not be stored or maintained at the investigation site. Following case conclusion, the study product shall be returned to sponsor. Inventory accountability will be managed and tracked by sponsor and reported to FDA as a component of the annual reporting requirements. Records pertaining to device shipment shall be maintained by sponsor with copies of device receipt invoices shipped to the site maintained in the respective site's administrative files. Device shipping invoices shall include the name of the consignee, type and quantity of device, date of shipment, and the lot number.

The site primary investigator is responsible for ensuring that investigational devices are made available only to site personnel who are authorized to access them and only to subjects under the Investigator's or sub-Investigator's supervision.

At the completion of the clinical investigation, any investigational product present at the site must be returned to Spineology. Further, a complete, and final, device accountability and reconciliation will be performed by Spineology at investigation conclusion and reported to FDA in accordance with Federal regulation.

10.0 DATA COLLECTION FORMS

The following patient-centric forms shall be used to record data in this investigation. Case report forms (CRFs) shall be completed accurately and in a timely manner. The Principal Investigator at each study site is responsible for oversight of the completion and submission of all clinical data collect at the respective site. For this investigation, data will be collected electronically and in compliance with the Code of Federal Regulations Title 21 Part 11.

The electronic version of the CRF is referred to as the eCRF. The eCRFs displayed in the electronic data capture (EDC) system implemented for this investigation yields additional functionality and form prompting beyond the basic information identified for capture in the paper version of the CRF. The eCRF is completed by the site in the EDC system. The paper version of the forms is provided to investigative sites in the form of worksheets for ease of use. The Inclusion/Exclusion worksheet and the Patient Survey worksheet may function as source documentation and shall be treated accordingly. The site shall provide the sponsor with redacted copies of all supporting source documentation as required to support centralized monitoring capabilities. Sample CRFs are provided as **Appendix VII**.

Screening Log – This log will record each subject enrolled into the investigation. It will additionally include patients screened for potential inclusion that fail to meet study entrance criteria. For screen failures, minimal information is collected to ensure compliance with HIPAA guidelines and to protect patient confidentiality. The eScreening Log should be updated on a regular basis by the site.

Inclusion/Exclusion Entrance Checklist – This form will be used to screen subjects for study entrance criteria to confirm the individual is an appropriate candidate for study participation. The eCRF should be entered in the EDC system as soon as reasonable but no later than 10 working days of subject enrollment.

Baseline/Pre-op History Form – This form captures relevant baseline information such as demographics, diagnosis for procedure, spinal treatment (conservative measures and surgical intervention) history, work status, etc. The eCRF should be entered in the EDC system within 10 working days of subject enrollment.

Patient Survey – This survey form collects subjective data consisting of pain rating on a Visual Analog Scale (VAS) for the low back, right leg, left leg and iliac crest as applicable (iliac crest completed at post-op intervals only for subject who underwent iliac crest graft harvest). The survey additionally contains a 10-question Oswestry Disability Index (ODI) to assess low back function and an SF-36 health questionnaire to assess mental and physical components. Lastly, this form allows the subject to rate their level of satisfaction with their surgical outcome and is to be completed only at the post-op follow-up intervals. The eCRF should be entered in the EDC system within 10 working days of the study visit date.

Pain Medication Log – The pain medication log shall be completed at baseline and reviewed at each subsequent study interval follow-up examination. The log shall be updated for changes in pain medication use (start, stop, changes in dosing) as compared to the previous study interval visit. Beyond identifying the prescription information (i.e. medication name, strength and frequency of use), the site shall specify if the pain medication is prescribed for treatment of low back pain or for other reasons. The eLog should be reviewed/updated in the EDC system within 10 working days of the study visit date.

Neurological Evaluation – This form captures relevant neurological testing for the lumbar spine (L2 – S1). Neurological testing includes assessment of bilateral lower extremity deep tendon reflexes (knee and ankle), muscle strength tested against resistance (hips, knees, ankles, and feet), and lumbosacral dermatome sensation (low back, thighs, calves, and feet). The eCRF should be entered in the EDC system within 10 working days of the study visit.

Surgery/Hospitalization – This form records relevant information regarding the study procedure including hospitalization duration, device detail, supplemental fixation detail and operative/intraoperative/postoperative findings. The eCRF should be entered in the EDC system within 10 working days of the subject discharge date.

Follow-Up Evaluation – This form captures relevant information regarding postoperative subject medical care, tobacco use, alcohol consumption, work status and occurrence of adverse events. The eCRF should be entered in the EDC system within 10 working days of the study visit.

Long-Term Follow-Up Questionnaire – This self-administered patient questionnaire captures relevant information regarding postoperative subject tobacco use, alcohol consumption, work status and safety information (occurrence of additional surgical intervention). In the event a subject identifies supplemental surgical intervention has occurred, the study site shall complete a corresponding adverse event form after obtaining the necessary and appropriate information. The questionnaire eCRF should be entered in the EDC system within 10 working days of completed form receipt.

Adverse Event (AE) – This form shall be entered into the EDC system as soon as reasonable for any subject presenting with an adverse event. Beyond eCRF completion, the site shall forward copies of redacted source documentation that support the AE to the sponsor. As noted above, the eCRF shall be entered in the EDC system as soon as reasonable but not greater than 15 working days of discovery of the event. The source documentation copies shall ideally be forwarded to Spineology within 15 working days of the discovery of the event.

Protocol Deviation (PD) – This form documents deviations from the study protocol. Protocol deviations shall be entered into the EDC system within 5 working days of the discovery of the deviation.

Subject Discontinuation (SD) – This form documents a subject's decision to withdraw from the investigation or an investigator's determination to discontinue a subject from study participation. The SD form shall be entered into the EDC system within 15 working days of the discontinuation notification.

Unanticipated Adverse Device Effect (UADE) – The UADE form records any unexpected adverse device effects experienced by a study subject. The investigator is required to notify the sponsor as soon as possible but not later than 10 working days after discovery of the UADE. The UADE form is entered into the EDC system by the site.

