- **Unknown:** An adverse event that cannot be determined to have a causal relationship with either the device or procedure will be classified as unknown.

It is anticipated that resultant of the defined criteria for each relatedness determination, few adverse events will be categorized as “Other”. The severity of events will be classified by the DMC as described in the following two sections.

8.2 **Serious Adverse Event**

The DMC will first determine whether an AE is serious. A Serious Adverse Event, corresponding to FDA’s definition, is an adverse event that results in one of the following outcomes:

- requires hospitalization,
- prolongs hospitalization,
- is life-threatening,
- results in a congenital anomaly/birth defect, or
- results in death.

8.3 **Event Severity**

The DMC will adjudicate the severity of each AE. Severity is categorized as follows:

- **Severe Adverse Event:** Significant impairment of functioning; subject is unable to carry out usual activities. A severe AE requires treatment or intervention.
- **Moderate Adverse Event:** Subject experiences sufficient discomfort to interfere with or reduce their usual level of activity. A moderate AE requires treatment.

- **Mild Adverse Event:** Subject is aware of event or symptom, but event/symptom is easily tolerated. A mild AE may not require treatment.

The Clinical Event Committee shall be convened on a quarterly basis through the duration of the investigation to formally review and adjudicate study events. The DMC Chairperson shall perform an interim (continuous) review of adverse events prior to conducting the quarterly committee review(s). The Chairperson may convene a Committee meeting at his/her discretion at any time to ensure subject safety is adequately protected.

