9.4 DATA MONITORING COMMITTEE (DMC)

An independent Data Monitoring Committee will be established for this investigation and will function as an advisory group to provide independent oversight of the investigation and to ensure patient safety. The DMC shall be comprised of no less than three (3) physician consultants of appropriate training, expertise and experience in the spinal discipline and a biostatistician. A DMC Chairperson shall be designated to preside over DMC meetings. The DMC may function in the role of a Data Safety Monitoring Board (DSMB) and as a Clinical Events Committee (CEC). The complete DMC Charter is provided as **Appendix V**.

DMC DSMB primary responsibility is to ensure subject safety. Additional DMC DSMB responsibilities may include, but are not limited to, review of interim analyses of outcomes, safety data summaries and study performance information. In addition, the DMC DSMB may provide recommendations relative to the study design, stopping rules for trial conduct, and determinations for continuance, modification, or termination of investigation conduct. DMC DSMB meetings will be conducted no less than annually.

DMC CEC responsibilities include review and adjudication of all adverse events reported for this investigation. The DMC CEC shall adjudicate events for seriousness, relatedness and severity. The DMC CEC shall review all events for potential UADE occurrence. DMC CEC meetings shall be conducted on a quarterly basis throughout the duration of this investigation.

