Study-Related Event – An event that meets the definition of an Adverse Event and in addition is determined to have a causal relationship to the study and/or attributable to study participation. The application of a Study-Related Adverse Event status is determined by the Data Monitoring Committee (DMC) as a component of the adjudication process. While all events regardless of status, categorization or relatedness are adjudication by the DMC and reported to FDA, only those events determined to be Study-Related Adverse Events will be included in the final statistical analysis for this trial.

Unknown Related AE – An adverse event that cannot be determined to have a causal relationship with either the investigational device, supplemental fixation hardware or its components, general surgery, or other relatedness.

Unanticipated Adverse Device Effect (UADE) – Any serious adverse effect on health or safety, any life-threatening problem or death caused by, or associated with, a device, if that effect, problem or death was not previously identified in nature, severity or degree of incidence in the application; or any other unanticipated serious problem associated with a device that relates to the rights, safety, or welfare of subjects.

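### Section 10 sets no faster reporting limit for serious adverse events than for others (15 working days), so a UADE that the site does not flag can come to light late

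*Combined protocol and SAP*

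**What the plan says.** Section 10.0 (Adverse Event) applies one rule to all events: "This form shall be entered into the EDC system as soon as reasonable for any subject presenting with an adverse event", with an outer limit worded "as soon as reasonable but not greater than 15 working days of discovery of the event". Supporting source documents "shall ideally be forwarded to Spineology within 15 working days of the discovery of the event", so their timing is a target and not a requirement.

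The UADE entry in the same section reads: "The investigator is required to notify the sponsor as soon as possible but not later than 10 working days after discovery of the UADE". Section 11.0 defines a UADE in terms of serious effects, beginning "Any serious adverse effect on health or safety, any life-threatening problem or death caused by, or associated with, a device", where the effect had not been previously identified, and adds other unanticipated serious problems.

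Two safeguards sit with the committee. Section 9.4 states: "The DMC CEC shall review all events for potential UADE occurrence". Section 8.2 states: "The DMC will first determine whether an AE is serious". The committee meets quarterly for adjudication (sections 8.3 and 9.4). Its chairperson reviews events continuously in between and may convene a meeting at any time (section 8.3), but no time limit is set for that review.

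**The concern.** UADEs are drawn from serious, device-associated events, yet the form that brings such an event to the sponsor and the committee may be entered later than a UADE notice would be due. For an effect that the site recognises as a UADE this does no harm, because the 10-working-day duty applies directly. The weak point is the effect that the site does not recognise. There the committee's screen is the backstop, and it cannot begin until the event is reported.

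What is at stake is time in which further subjects may be implanted before an unrecognised device effect is assessed. The sponsor's prompt notification of FDA, IRBs and all investigators (section 15.0) is delayed in turn.

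The limits in section 10 also look out of order. A protocol deviation form is due within 5 working days of discovery, including minor deviations such as an out-of-window visit (section 12.0). Most visit forms are due within 10. A death or life-threatening event falls under the 15-working-day limit, the longest in the section, shared only with Subject Discontinuation.

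**Working it through.** The plan gives no figure of its own to reproduce. The check compares the stated limits and then converts them into implantations.

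**Inputs**
- Adverse event form: at most 15 working days from discovery of the event (section 10.0).
- UADE notice: at most 10 working days from discovery of the UADE (section 10.0).
- Enrolment: at most 102 subjects over 18 to 24 months (section 2.3).
- Assumptions: five working days a week, no holidays, 30.4 days a month, even accrual, and implantation at the rate of enrolment.

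**Gap between the limits**
- With both clocks started on the day the site learns of the event: 15 − 10 = 5 working days.
- With the UADE clock started only on recognition: no gap can be computed, because for an unflagged event that clock is not yet running. The event may still arrive as late as working day 15.

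**Calendar time**
- 5 working days = 7 calendar days.
- 15 working days = 21 calendar days.

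**Accrual**
- 102 / 24 = 4.25 a month; 102 / 18 = 5.67 a month.

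**Further implantations during enrolment**

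| Interval | At 4.25 a month | At 5.67 a month |
|---|---|---|
| 5-working-day gap | 4.25 × 7 / 30.4 = 1.0 | 5.67 × 7 / 30.4 = 1.3 |
| Full 15 working days | 4.25 × 21 / 30.4 = 2.9 | 5.67 × 21 / 30.4 = 3.9 |

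As a sensitivity check, section 2.3 plans 0.85 subjects per site per month. With all 10 sites active that is 8.5 a month, which gives 8.5 × 7 / 30.4 = 2.0 and 8.5 × 21 / 30.4 = 5.9. This rate applies only while every site is enrolling. After enrolment closes, both figures are zero.

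**Search for a faster route.** Sections 8, 9.4, 10, 11, 15 and 16 contain no reporting limit specific to serious events.

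**The case against.** **The two clocks differ.** One runs from discovery of the event, the other from discovery of the UADE. A site that has not recognised a UADE has arguably not discovered one. This stands: the 5-day overrun depends on a common start, and on the other reading only late detection remains.

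**Readings that go too far.** A reader might infer that the committee's screen cannot meet the plan's own deadline. The documents do not support that: the 10 working days bind the investigator's notice to the sponsor, and no deadline is set for the committee's review. Nor do the two limits contradict each other, since a recognised UADE has its own shorter duty. A reader might also attribute 3 to 4 implantations to the mismatch. That figure covers all 15 working days, including the 10 that the UADE rule itself allows.

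**Fifteen days is an outer limit, and earlier routes exist.** Entry is to be made as soon as reasonable. The Follow-Up Evaluation form records adverse events and is due within 10 working days of a visit. The Surgery/Hospitalization form is due within 10 working days of discharge. Centralized monitoring treats serious adverse events as a high-risk indicator (section 16.0). These routes make the delay permitted, not inevitable. The two forms are tied to visits or discharge, and neither is linked to committee review. Remote monitoring depends on data having been submitted. None assures an earlier report of an event discovered between visits.

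**Unseen appendices.** The DMC Charter (Appendix V) and the sample case report forms (Appendix VII) are not in the text reviewed and may hold a serious-event limit. It would therefore be too strong to say that no such limit exists anywhere; if one does, section 10 should cite it.

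**Conclusion.** The point holds as a gap in reporting design. A site that follows section 10 exactly may take until working day 15 to report a death or life-threatening event found between visits, and the committee's seriousness decision and UADE screen wait on that report. The overrun against the UADE limit is 5 working days on a common clock start; otherwise detection is late without a formal breach.

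The size is modest and confined to enrolment: about one further implantation for the gap, and about 3 to 4 for the full period, at even accrual. No endpoint, sample size or planned analysis is affected. The change should still be made, because the present rule allows a safety delay that is cheap to remove.

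**What to change.** In section 10.0, add a separate rule: an event that the site provisionally judges to meet one of the section 8.2 outcomes is notified to the sponsor and the committee chairperson, with the source documents then available, within a limit shorter than the 10-working-day UADE limit and counted from discovery of the event. Keep 15 working days for other events. State that the final decision on seriousness remains with the committee, so that the provisional check does not conflict with section 8.2, and align the wording with the DMC Charter (Appendix V).

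The cost is a provisional seriousness check at the site, which the protocol text does not now ask for, training on it, and faster reporting for what should be a small number of events.

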11.0 DEFINITIONS

Adverse Event – A secondary disease or condition that develops in addition to, or at an increased rate or severity from, the expected response to treatment, necessitating further evaluation and treatment by a physician. All adverse events, whether related or unrelated to the device or procedure, shall be captured and reported. Further, all adverse events will be adjudicated by the Data Monitoring Committee and reported to FDA per protocol.

Case Report Form (CRF)/Electronic Case Report Form (eCRF)/CRF Worksheet –

- **CRF** – A document designated to record protocol required information for each subject participating in an investigation. A CRF may be provided to sites in paper copy or electronic copy. A paper CRF may be used as a worksheet providing the captured information is recorded in the electronic database.
- **eCRF** – A database equivalent electronic version of the CRF.
- **CRF Worksheet** – A paper version of a CRF used to collect data that will be entered into the eCRF. Worksheets shall be maintained in the relevant study subject's binder at the investigation site.

Centralized Monitoring – A remote evaluation carried out by sponsor personnel or representatives (e.g., clinical monitors, data management personnel, or statistician) at a location other than the site(s) at which the clinical investigation is being conducted.

Device Related – An adverse event that results from the presence, performance or implantation procedure of the investigational device (SIFS mesh).

Enrolled – For this investigation, a subject is considered enrolled after meeting all study entrance criteria, has confirmed agreement to participate in the investigation as documented through completion of the informed consent process, and has been assigned a surgical procedure date. Further, it is expected that prior to enrollment, the investigational site will have successfully negotiated the precertification process as required for pertinent insurance carriers, and obtained documentation of the carrier's precertification approval.

Extended Hospitalization – Increased duration of hospitalization based on determination of the treating investigator.

Functional Disability – In this investigation, functional disability is defined as the subject's self-rated score on the Oswestry Disability Index. The ODI is a commonly used 10 question instrument for assessing patients with back pain. The greater the score achieved, the greater the functional disability. A lower ODI score indicates less back disability (greater back function). A 15 point difference compared to baseline is considered clinically significant.

Hardware Related AE – An adverse event that results from the presence, performance or implantation of the supplemental fixation device hardware or its components.

Informed Consent – A process by which a subject voluntarily confirms his or her willingness to participate in a particular investigation, after having been informed of all aspects of the investigation that are relevant to the subject's decision to participate. Informed consent is

documented by means of a written, signed, and dated informed consent form approved by the site's reviewing IRB.

Institutional Review Board (IRB) – An independent body (a review board or a committee, institutional, regional, or national (centralized) constituted of medical/scientific professionals and non-medical/non-scientific members, whose responsibility it is to ensure the protection of the rights, safety, and well-being of human subjects involved in an investigation and to provide public assurance of that protection, by among other things, reviewing and approving/providing favorable opinion on the investigation protocol, the suitability of the investigator(s), facilities, and the methods and materials to be used in obtaining and documenting informed consent of the investigation subjects.

Low Back Pain (LBP) – For this investigation, LBP is defined as the self-rated score a subject indicates on a Visual Analog Scale during normal daily activities. When interpreting the VAS, a higher score indicates a greater level of pain severity and a lower score indicates a lesser severity of pain. LBP is captured on a 100mm VAS. A 20mm difference when compared to baseline is considered clinically significant. The same measurement system/guideline is employed for leg pain.

Not Study-Related AE – An event adjudicated by the DMC CEC and determined to not have a causal relationship with either the device or the procedure.

Observation – An observation is an event adjudicated by the DMC CEC and determined to be a non-event and did not require treatment.

On-Site Monitoring – An in-person evaluation of the clinical investigation site that is conducted by sponsor personnel or representatives.

Other Related AE – An adverse event that occurs and is determined to have a relatedness that is not device, hardware general surgery or unknown relatedness.

Procedure Related AE – An adverse event that occurs as a result of the surgical procedure. A procedure related AE may occur as a result of one or more of the following and shall be specified as such for analysis and reporting purposes:

- *Procedure – Device*: Occurs due to the implantation procedure for the investigational device (SIFS mesh)
- *Procedure – Hardware*: Occurs due to the implantation procedure for the supplemental fixation
- *Procedure – General Surgery*: Occurs as a result of the general surgical procedure

Removal – A surgical procedure in which all of the original system (intervertebral device plus supplemental fixation) confirmation is removed, with or without replacement.

Re-Operation – Any surgical procedure at the treated level that does not include removal, modification, or addition of any implanted components.

Revision: Device – A surgical procedure that adjusts or in any way modifies or removes part of the original intervertebral implant configuration, with or without replacement of a component. A revision may also include adjusting the position of the original configuration.

Revision: Hardware – A surgical procedure that adjusts or in any way modifies or removes part of the original supplemental fixation implant configuration, with or without replacement of a component. A revision may also include adjusting the position of the original configuration.

Risk-Based Monitoring – A dynamic assessment procedure that systematically approaches clinical trial monitoring of the individual and global investigation sites, evaluating for data integrity, observable trending and compliance risks that may be associated with the clinical investigation during the trial lifecycle.

Serious Adverse Event (SAE) – An adverse event that requires hospitalization, prolongs or extends the hospitalization, is life-threatening, results in a congenital anomaly/birth defect, or results in death. The device-relatedness or procedure-relatedness of such an event will be adjudicated by the DMC.

Study-Related Event – An event that meets the definition of an Adverse Event and in addition is determined to have a causal relationship to the study and/or attributable to study participation. The application of a Study-Related Adverse Event status is determined by the Data Monitoring Committee (DMC) as a component of the adjudication process. While all events regardless of status, categorization or relatedness are adjudication by the DMC and reported to FDA, only those events determined to be Study-Related Adverse Events will be included in the final statistical analysis for this trial.

Unknown Related AE – An adverse event that cannot be determined to have a causal relationship with either the investigational device, supplemental fixation hardware or its components, general surgery, or other relatedness.

Unanticipated Adverse Device Effect (UADE) – Any serious adverse effect on health or safety, any life-threatening problem or death caused by, or associated with, a device, if that effect, problem or death was not previously identified in nature, severity or degree of incidence in the application; or any other unanticipated serious problem associated with a device that relates to the rights, safety, or welfare of subjects.

